8.3.2 Proportion and Confidence Interval for Proportions

The proportion is calculated by the following formula unless otherwise instructed:

$$\text{Proportion(%) = } \frac{\text{Applicable subjects}}{\text{Subjects in the analysis population}} \times 100$$

$$\text{AE(%) = } \frac{\text{The number of subjects with AEs}}{\text{Subjects in the analysis population}} \times 100$$

For two-sided 95% CI for proportion, exact test will be used.

Regarding sample code, refer to Appendix 1.

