11.1 Primary Efficacy Endpoint

11.1.1 Cumulative Number of Weeks of Platelet Response

Population: Full Analysis Set, Per Protocol Set

Target Phases: Core Phase

Analysis items:

- The cumulative number of weeks in which the platelet count is $\geq 50 \times 10^9/L$ during 26 weeks of treatment in the absence of rescue therapy for each subject

Contents:

- Descriptive statistics and 95% CI of mean of the cumulative number of weeks of platelet response during 26 weeks of treatment in the absence of rescue therapy is calculated.

Definitions:

- Platelet response: platelet count of $\geq 50 \times 10^9/L$

- Cumulative number of weeks of platelet response during 26 weeks of treatment in the absence of rescue therapy is calculated by the formula: (sum of platelet response duration)/7= sum of (last day platelet response - the first day platelet response +1)/7.
- All scheduled and unscheduled visits will be used. If the subject missed a visit, the visit date will be imputed based on analysis target date.
- Platelet response will be defined with consideration referring the handling of data as described in 3 cases below:
 - 1. Subjects who have missing platelet assessments at any scheduled visit of interest will be considered as non-responders at that time point.
 - 2. Subjects who use rescue therapy at any time during the 26-week treatment period will be considered as non-responders for all subsequent days after rescue therapy start date.
 - 3. Subjects who discontinue the study or who are lost to follow-up before 26 weeks will have all subsequent unobserved scheduled platelet assessments at the scheduled time points as having “missing” platelet values.

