11.2 Key Secondary Efficacy Endpoint

11.2.1 Platelet Response Rate at Visit 4 (Day 8)

Population: Full Analysis Set, Per Protocol Set

Target Phases: Core Phase

Analysis items: - Platelet response rate at Visit 4 (Day 8)

Contents: - The number of platelet response (Yes/No) at Visit 4 (Day 8) and its proportion with 95% CI is calculated.

Definitions: - Responders (Yes): Subjects with a platelet count $\geq 50 \times 10^9 / L$ at Visit 4 (Day 8) in the absence of rescue therapy before or on Visit 4 (Day 8).
- Non-responders (No): Subjects with a platelet count $< 50 \times 10^9 / L$ at Visit 4 (Day 8) or with missing platelet counts at Visit 4 (Day 8) or use of a rescue therapy before or on Visit 4 (Day 8).

- Regarding the efficacy data handling, refer to 3 cases below:

- 1. Subjects who have missing platelet assessments at Visit 4 (Day 8) will be considered as non-responders.
- 2. Subjects who use rescue therapy before or on Visit 4 (Day 8) will be considered as non-responders at Visit 4 (Day 8).
- 3. Subjects who discontinue the study or who are lost to follow-up before or on Visit 4 (Day 8) will be considered as non-responders at Visit 4 (Day 8).

- Regarding 95% CI for binomial proportions, refer to [8.3.2 Proportion and Confidence Intervals for proportions](#)

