11.3 Other Efficacy Endpoints

11.3.1 Durable Platelet Response

Population: Full Analysis Set, Per Protocol Set

Target Phases: Core Phase

Analysis items: - Durable platelet response

Contents: - The number of responders/non-responders and its proportion with 95% CI is calculated.

Definitions: - Responders (Yes): Subjects who have at least 6 of 8 (i.e., $\geq 75\%$) weekly platelet counts $\geq 50 \times 10^9 / L$ during the last 8 weeks (from Visit 15 (Week 19) to Visit 22 (Week 26)) of treatment over the 26-week treatment period and not taking any rescue therapy.
- Non-responders (No): Subjects who have less than 6 weekly platelet counts $\geq 50 \times 10^9 / L$ during the last 8 weeks over the 26-week treatment

- period or taking any rescue therapy.
- Regarding the data handling:
 - 1. Subjects who have missing platelet assessments at scheduled visits of interest will be considered as non-responder at any given time point.
 - 2. Subjects who use rescue therapy at any time during 26-week treatment period will be considered as non-responders for all subsequent days after rescue therapy start date.
 - 3. Subjects who discontinue the study or who are lost to follow-up before 26 weeks will have all subsequent unobserved scheduled platelet assessments at the scheduled time points as having “missing” platelet values.
- Regarding 95% CI for binomial proportions, refer to [8.3.2 Proportion and Confidence Intervals for proportions](#).
- Regarding Rescue therapy, refer to table [11.3.9 Subjects with any Rescue Therapy Use](#)

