11.3.6 Platelet Response by Visit

| | |
|-----------------|--|
| Population: | Full Analysis Set, Per Protocol Set |
| Target Phases: | Core Phase |
| Visit: | Visit 3 (Day 5) - Visit 22 (Week 26) |
| Analysis items: | 
- Platelet Response by Visit |
| Contents: | 
- The number of subjects with platelet response (Yes/No) at each analysis visit are calculated based on subjects with assessment available at the visit (n). |
| Definitions: | 
- Responders (Yes): Subjects who have platelet count $\geq 50 \times 10^9/L$ and in the absence of rescue therapy.- Non-responders (No): Subjects who have platelet count $< 50 \times 10^9/L$ or have platelet count $\geq 50 \times 10^9/L$ that occurs within 8 weeks after rescue therapy usage.- Regarding the efficacy data handling, refer to the case below:
➤ 1. Subjects who have missing platelet assessments will be excluded from the summary at that visit. |

- 2. If subjects use rescue medication, subjects will be considered as non-responders from the rescue medication start date to rescue medication end date + 8 weeks.
- The denominator to calculate the proportion is the number of subjects in target population by each analysis visit with non-missing data.

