11.3.7 Complete Platelet Response Rate by International Working Group (IWG) by Visit

| | |
|-----------------|---|
| Population: | Full Analysis Set, Per Protocol Set |
| Target Phases: | Core Phase |
| Visits: | Visit 3 (Day 5) - Visit 22 (Week 26) |
| Analysis items: | 
- Complete platelet response by IWG |
| Contents: | 
- The number and proportion of subjects with a complete platelet response (Yes/No) at each analysis visit are calculated based on subjects with assessment available at the visit (n). |
| Definitions: | 
- Complete platelet response:
➤ Responders (Yes): Subjects with a platelet count $\geq 100 \times 10^9/L$ and in the absence of bleeding or rescue therapy.➤ Non-responders (No): Subjects with a platelet count $< 100 \times 10^9/L$ or the presence of bleeding. Platelet assessment with any bleeding event at the same visit or a platelet count that occurs within 8 weeks after rescue therapy is considered as nonresponse.- Regarding the efficacy data handling, refer to the cases below:
➤ 1. Subjects who have missing platelet assessments will be excluded from the summary at that visit.➤ 2. If subjects use rescue medication, subjects will be considered as non-responders from the rescue medication start date to rescue medication end date + 8 weeks.➤ 3. Subject who has WHO bleeding scale grade ≥ 1 will be considered as non-responder at that visit.- The denominator to calculate the proportion is the number of subjects in target population by each analysis visit with non-missing data. |

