11.3.8 Platelet Response Rate by International Working Group (IWG) by Visit

Population: Full Analysis Set, Per Protocol Set

Target Phases: Core Phase

Visits: Visit 3 (Day 5) - Visit 22 (Week 26)

Analysis items: - Platelet response by IWG

Contents: - The number and proportion of subjects with a platelet response (Yes/No) at each analysis visit are calculated based on subjects with assessment available at the visit (n).

Definitions: - Platelet response:

- Responders (Yes): Subjects with a platelet count $\geq 30 \times 10^9/L$ and at least a 2-fold increase in baseline count and absence of bleeding or rescue therapy.
- Non-responders (No): Subjects with a platelet count $< 30 \times 10^9/L$ or less than a 2-fold increase in baseline count, or the presence of bleeding or rescue therapy. Platelet assessment with any bleeding event at the same visit or a platelet count that occurs within 8 weeks after rescue therapy is considered as nonresponse.

- Regarding the efficacy data handling, refer to the cases of [11.3.7 Complete Platelet Response Rate by International Working Group \(IWG\) by Visit](#)

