11.3.11 Worst Post-baseline Bleeding Grade (WHO Bleeding Scale)

Population: Full Analysis Set, Per Protocol Set (for Core Phase only)

Target Phases: Core Phase, Extension Phase

Analysis items: - The worst post-baseline bleeding grade based on WHO Bleeding Scale

Contents: - The number and proportion of subjects with the worst post-baseline bleeding grade (WHO Bleeding Scale) reported in Core Phase (up to End of Study visit (excluding dose tapering and follow-up period)) and in Extension Phase (from E1 (Month 1) to Last Visit).

Definitions: - WHO Bleeding Scale:
 Grade 0: No bleeding
 Grade 1: Petechial bleeding
 Grade 2: Mild blood loss (clinically significant)
 Grade 3: Gross blood loss
 Grade 4: Debilitating blood loss.
- Worst post-baseline bleeding grade (WHO Bleeding Scale) is the highest grade reported after baseline.
- The denominator is the number of subjects in the analysis population.

12 Pharmacokinetic Concentrations

Blood samples for serial PK assessments will be collected during Visit 5 (Week 2) and Visit 10 (Week 10) of the Core Phase. Regardless of the subject's current treatment regimen (e.g., once daily, three times a week), the serial PK sampling at Visit 5 (Week 2) and Visit 10 (Week 10) must occur on a day the subject is scheduled to take their dose of study drug. Therefore, if study drug has been held or the dosing regimen has changed within the past week, the serial PK samples should be collected at a visit later than Visit 5 (Week 2) or Visit 10 (Week 10). This is to ensure that serial PK samples will be obtained when the subject has been on a stable dose for at least 1 week.

During the serial PK sampling visits, subjects will have three blood samples (2 mL each) drawn: pre-dose; between 2 and 4 hours post-dose; and between 6 and 8 hours post-dose.

Blood samples for sparse PK assessments (2 mL each) will be collected while the subject is at the clinic during Visit 4 (Day 8), Visit 7 (Week 4), Visit 8 (Week 6), Visit 13 (Week 16) and Visit 22 (Week 26)/End of Treatment (EOT) (2 mL each).

The pharmacokinetic sampling schedule is presented in following table:

| Study Day | Sparse/Serial | Sampling Times |
|---------------------------|---------------|--|
| Visit 4 (Day 8) | Sparse | During clinic visit |
| Visit 5 (Week 2) | Serial | 
 • Pre-dose • Between 2 and 4 hours post-dose • Between 6 and 8 hours post-dose |
| Visit 7 (Week 4) | Sparse | During clinic visit |

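### By-visit IWG response rates omit subjects with no platelet count, so they can rise as treatment failures leave, and no planned IWG rate counts those subjects as nonresponders

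*SAP*

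**What the plan says.** Three by-visit analyses use observed cases only. SAP 11.3.6 (platelet response) and 11.3.7 (IWG complete response) both drop a subject who has no count: "Subjects who have missing platelet assessments will be excluded from the summary at that visit". Both then define the denominator to match: "The denominator to calculate the proportion is the number of subjects in target population by each analysis visit with non-missing data". SAP 11.3.8 (IWG response) works from subjects assessed at the visit and refers to 11.3.7 for data handling.

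The other platelet-response analyses take the opposite line:

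- Primary endpoint, 11.1.1: "Subjects who have missing platelet assessments at any scheduled visit of interest will be considered as non-responders at that time point".
- Day 8 key secondary endpoint, 11.2.1: "Subjects who have missing platelet assessments at Visit 4 (Day 8) will be considered as non-responders".
- Durable response, 11.3.1: "Subjects who have missing platelet assessments at scheduled visits of interest will be considered as non-responder at any given time point".
- Maximum duration, 11.3.2, which refers to 11.1.1 for data handling.

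The general rule in SAP 8.3.2 divides by all subjects in the analysis population, but allows exceptions: "The proportion is calculated by the following formula unless otherwise instructed". Sections 11.3.6 to 11.3.8 use that exception and give no reason. The bleeding summary in 11.3.11 keeps the general rule: "The denominator is the number of subjects in the analysis population".

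**The concern.** A subject who leaves the study has no later counts and drops out of the denominator at every later visit. If those who leave are mostly nonresponders, the percentage rises although the number of responders does not.

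The plan makes that kind of exit likely to be related to outcome. SAP 9.2 lists failure to respond at dose Level 6 among the reasons for discontinuing the study as well as treatment. Protocol 5.3 says that subjects who terminate early are not replaced. SAP 3.3.1, writing about the primary endpoint, classes unobserved counts after exit as missing.

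Both IWG outcomes are named efficacy endpoints (protocol 3.3, SAP 3.3.3) and are analysed only in 11.3.7 and 11.3.8. They use different thresholds and also require absence of bleeding, so the analyses at 50 × 10⁹/L cannot stand in for them. In a single-arm study there is no comparator whose own attrition would help a reader judge a rising curve. The report would also set side by side response rates built on two different missing-data rules.

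**Working it through.** **Inputs**

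- N = 19, from SAP section 6 and protocol 10.2.5. The figure reproduces as the smallest n for which 12.0 − 1.96 × 8.75/√n is at least 8.02: (1.96 × 8.75/3.98)² = 18.57, rounded up to 19. Here it serves only as the number of subjects. SAP 4.2 says at least 19, so an assumed N = 22 is shown as well.
- R, the responders observed at a visit, and k, the subjects with no count there. The documents give neither, so all values of R and k below are assumptions.

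**Formulas**

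- SAP rate: R/(N − k).
- Missing-as-nonresponse rate: R/N.
- Ratio of the first to the second: N/(N − k). It is 1 at k = 0 and above 1 otherwise, so with any responders the SAP rate is never the lower of the two.

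**Ratio**

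| k | N = 19 | N = 22 (assumed) |
|---|---|---|
| 0 | 1.000 | 1.000 |
| 1 | 19/18 = 1.056 | 22/21 = 1.048 |
| 2 | 19/17 = 1.118 | 22/20 = 1.100 |
| 4 | 19/15 = 1.267 | 22/18 = 1.222 |

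**Rates at N = 19**

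| k | R = 9, SAP rate | Gap from 9/19 = 47.4% | R = 5, SAP rate | Gap from 5/19 = 26.3% |
|---|---|---|---|---|
| 1 | 9/18 = 50.0% | 2.6 points | 5/18 = 27.8% | 1.5 points |
| 2 | 9/17 = 52.9% | 5.6 points | 5/17 = 29.4% | 3.1 points |
| 4 | 9/15 = 60.0% | 12.6 points | 5/15 = 33.3% | 7.0 points |

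Read down a column, the same nine (or five) subjects respond throughout. Only the denominator changes.

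**What the gap measures.** It equals inflation only if every subject without a count is a nonresponder. At the other extreme all of them would have responded, and the rate would be (R + k)/N. With R = 9 and k = 2 that is 11/19 = 57.9%, so the observed-case 52.9% lies between 47.4% and 57.9%. Missing-as-nonresponse is the lower bound.

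**Day 8.** SAP 11.2.1 and the Visit 4 row of 11.3.6 concern the same threshold and visit. With R = 9 and one missing count, 11.2.1 gives 9/19 = 47.4% and 11.3.6 gives 9/18 = 50.0%.

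**Does another rule close the gap?** Sections 11.3.6 to 11.3.8 count rescue users as nonresponders until 8 weeks after rescue ends. The SAP does not say whether this overrides exclusion for a missing count, so it cannot be relied on for a subject who has left. For response at 50 × 10⁹/L, 11.2.1 covers Day 8 and 11.3.1 covers Weeks 19 to 26 with missing as nonresponse. Nothing equivalent exists for either IWG endpoint.

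**The case against.** The strongest reply is that this is a choice of display, openly made. Section 8.3.2 permits exceptions, and the protocol attaches missing-as-nonresponse only to the primary and key secondary endpoints. The IWG rates are descriptive, with no test and no confidence interval. The number of responders and the n assessed are shown at each visit, and the FAS size is tabulated, so a reader can compute R/N. All of that stands: no rule is broken and nothing is concealed. But the percentage in the table, the one likely to be quoted, would still be the observed-case one.

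It can also be said that R and k are assumed and that missed visits need not be failures. Responders may miss a visit or leave for unrelated reasons, and the proposed rule would score them as failures. This stands too, and is why both rates should be shown. At N = 19 one subject is 5.3 points (1/19), so the gaps at k = 1 and k = 2 amount to about one subject or less, and the exact 95% interval for 9/19 (24.4% to 71.1%) contains every R = 9 value above. That interval describes sampling uncertainty. It does not remove a shift that goes in one direction when failures leave.

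Nobody can fail at Level 6 by Day 8, since all subjects start at Level 4. The Day 8 point is therefore one of consistency between two tables, not of failures leaving. An early leaver may contribute one nonresponse count at the end-of-treatment assessment, but is still excluded from later visits. Finally, changing the denominator does not align the rescue rules: 11.3.6 to 11.3.8 use the 8-week window, whereas 11.1.1 and 11.3.1 carry nonresponse forward for all later days. That difference would remain.

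**Conclusion.** The concern holds. As planned, both IWG rates can rise over visits through attrition alone, and no planned IWG rate counts those who left. With 19 subjects, the displayed rate exceeds the missing-as-nonresponse rate by a factor of 1.056, 1.118 or 1.267 when 1, 2 or 4 subjects lack a count. With 9 assumed responders that is 2.6, 5.6 or 12.6 points. The gap is smaller with fewer responders or a larger N, and nil if no count is missing. Reading it as bias assumes that those without counts are mainly nonresponders, which the listed exit reasons make plausible but do not establish.

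The weight is moderate. By-visit response at 50 × 10⁹/L (11.3.6) matters less, because other analyses partly cover it. The change should be made because it is cheap and follows the SAP's own convention.

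**What to change.** In SAP 11.3.7 and 11.3.8, and in 11.3.6 for consistency:

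1. Make the main rate at each visit the number of responders divided by all subjects in the FAS (or PPS), and count a subject with no platelet count at that visit as a nonresponder, including after exit. The denominator sentence in 11.3.11 can be reused.
2. Remove the exclusion case and the non-missing denominator from the main rate.
3. Keep the observed-case rate, with n per visit, as a separately labelled supplementary display.

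This needs SAP wording and one denominator change in programming, with no new data. The price is lower headline rates, and some responders who miss a single visit or leave for reasons unrelated to efficacy will be scored as nonresponders. Showing both rates lets the reader see how much depends on the missing counts.

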11.3.8 Platelet Response Rate by International Working Group (IWG) by Visit

Population: Full Analysis Set, Per Protocol Set

Target Phases: Core Phase

Visits: Visit 3 (Day 5) - Visit 22 (Week 26)

Analysis items: - Platelet response by IWG

Contents: - The number and proportion of subjects with a platelet response (Yes/No) at each analysis visit are calculated based on subjects with assessment available at the visit (n).

Definitions: - Platelet response:

- Responders (Yes): Subjects with a platelet count $\geq 30 \times 10^9/L$ and at least a 2-fold increase in baseline count and absence of bleeding or rescue therapy.
- Non-responders (No): Subjects with a platelet count $< 30 \times 10^9/L$ or less than a 2-fold increase in baseline count, or the presence of bleeding or rescue therapy. Platelet assessment with any bleeding event at the same visit or a platelet count that occurs within 8 weeks after rescue therapy is considered as nonresponse.

- Regarding the efficacy data handling, refer to the cases of [11.3.7 Complete Platelet Response Rate by International Working Group \(IWG\) by Visit](#)

11.3.9 Subjects with any Rescue Therapy Use

Population: Full Analysis Set, Per Protocol Set (for Core Phase only)

Target Phases: Core Phase, Extension Phase

Analysis items: - Rescue therapy (Yes/No)

Contents: - The number of subjects with rescue therapy (Yes/ No) and its proportion with 95% CI are calculated.

Definitions: - Rescue therapy (Yes): The number of subjects who use at least one rescue therapy after the first administration of study drug in each phase (Core Phase (26-week treatment period) or Extension Phase).

- If one subject takes the same therapy in both Core Phase and Extension Phase (e.g. the end date of rescue therapy in Core Phase is ongoing), that subject will be counted in Core Phase and Extension Phase respectively.
- The denominator to calculate the proportion is the target population (the number of subjects in Full Analysis Set/Per Protocol Set)
- Rescue therapy will be defined as the addition of any new ITP medication or medication to treat thrombocytopenia (examples below). TPO receptor agonists are not allowed as rescue therapy.

- Corticosteroids (ATC level 2 = “CORTICOSTEROIDS FOR SYSTEMIC USE”)
- Intravenous immunoglobulin (IVIg) therapy (ATC level 2= “IMMUNE SERA AND IMMUNOGLOBULINS”)
- Anti-D therapy (PT = “Anti-D (rh) immunoglobulin”)
- Mycophenolate mofetil (PT = “Mycophenolate mofetil”)
- Azathioprine (PT = “Azathioprine”)
- Danazol (PT = “Danazol”)
- Cyclosporin A (PT = “Ciclosporin”)
- Platelet transfusion (concomitant procedure as “TRANSFUSIONS”)
- Any increase in baseline dose of a concomitant ITP medication
- Regarding 95% CI for binomial proportions, refer to [8.3.2 Proportion and Confidence Intervals for proportions.](#)

11.3.10 Subjects with a Reduction/Discontinuation in use of Concomitant ITP Medications from Baseline

Population: Full Analysis Set, Per Protocol Set

Target Phases: Core Phase

Analysis items: - Reduction in use of concomitant ITP medications

- Discontinuation in use of concomitant ITP medications

Contents: - Calculate the number of subjects who have a reduction/discontinuation of Concomitant ITP medications after baseline.

For each item, the denominator is as below

| Items | The denominator of percentage |
|--|---|
| 
 • Reduction of Concomitant ITP medications after baseline • Discontinuation of Concomitant ITP medications after baseline | The number of subjects who used concomitant ITP medications at baseline |

Definitions: ITP medications are defined as the medications with ATC level 2 = “CORTICOSTEROIDS FOR SYSTEMIC USE”

Baseline ITP medications are defined as the ITP medications that are taken on the day of first administration; and concomitant ITP medications use at Core Phase are defined as ITP medications that start after the day of first administration and up to the last day of 26-week treatment period (excluding dose-tapering period) of Core Phase.

Only subjects with use of concomitant ITP medications at baseline will be included in the analysis. If a subject has use of concomitant ITP medication at baseline and has all post-baseline total daily doses for same medications (by PT) reduced without later increasing to the baseline or higher dose, or has no use of concomitant ITP medication post-baseline during 26-week

treatment, this subject is considered as having a reduction in use of concomitant ITP medication from baseline.

Subjects who discontinue all concomitant ITP medications before the last dose date of 26-week treatment will be considered as having a discontinuation of concomitant ITP medications.

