# 4.3.6 Follow-up Period (Visits 27 to 30)

During this period, subjects will be followed for 4 weeks after the last dose taken in the Dose-tapering Period. Subjects will return approximately every week for visits during this period and will have their final evaluations on the last day of the Follow-up Period. Platelet counts will be carefully monitored during this period for the recurrence of thrombocytopenia.

Subsequent upward titration or addition of concomitant ITP medication should be considered, athe Investigator's discretion, to prevent the recurrence of thrombocytopenia.

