# 5.3.1 Subjects with Study Drug Discontinuation

In both the Primary Investigation Phase (Core Phase) and the Extension Phase, study drug may be permanently discontinued at the discretion of the Investigator due to safety reasons, at the request of the subject, or if any of the following occur:

- Platelet count remains <30×10^9/L after more than 3 weeks at the maximum dose level (Level 6) (subjects can be discontinued after 7 days of therapy at the maximum dose level if they have dangerously low platelet counts in the opinion of the Investigator)
- Subjects who require rescue therapy more than 3 times or continuous rescue therapy for more than 3 weeks
- Excessive platelet count responses (> $400 \times 10^9$ /L) at the minimum dose level (Level 1)
- Treatment with certain ITP therapies/procedures, such as vinca alkaloids, cyclophosphamide, rituximab, splenectomy, or other TPO-RAs (eltrombopag, romiplostim).

If a subject discontinues study drug due to an AE, the Investigator will attempt to follow the event until it has resolved or stabilized.

If possible, a subject who discontinues treatment will complete the EOT assessments for the applicable phase and protocol-specified information will be collected. The primary reason for discontinuation and all other reason(s) contributing to the subject's discontinuation from study drug(s) as well as the date of last dose should be collected in the CRF.

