## **6.5.1** Excluded Medications and/or Procedures

The following medications and/or procedures are excluded:

- Platelet transfusion within 7 days before the first dose of study drug.
- Antifibrinolytic agents (aprotinin, tranexamic acid, and aminocaproic acid) and recombinant activated factor VII are prohibited during the treatment phase of the study.
- Moderate or strong dual inhibitors/inducers of CYP2C9 and CYP3A4 are prohibited during the study due to PK interactions with avatrombopag (see Appendix D for examples).
- Heparin, warfarin, factor Xa inhibitors, direct thrombin inhibitors, fresh frozen plasma and cryoprecipitate, chronic antiplatelet therapy (>4 weeks) with aspirin, clopidogrel sulfate, prasugrel hydrochloride, ticlopidine, or glycoprotein IIb/IIIa antagonists are prohibited during the Primary Investigation Phase (Core Phase) of the study.
- Some ITP therapies/procedures, such as vinca alkaloids, cyclophosphamide, rituximab, splenectomy, and other TPO-RAs (eltrombopag, romiplostim) are prohibited during the Primary Investigation Phase (Core Phase) due to their potential to confound efficacy results. Subjects requiring these therapies will be discontinued from the study.
- Enrollment in another clinical study with any investigational drug or device within 30 days
  of Screening or during the study; however, participation in observational studies is
  permitted.

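### The primary endpoint has no explicit nonresponse rule for platelet counts observed after splenectomy or another prohibited ITP therapy has begun

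*SAP*

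**What the plan says.** **Nonresponse rules.** SAP 11.1.1 gives three. Case 1 makes a missing scheduled assessment a nonresponse. Case 2 says that subjects who use rescue therapy "will be considered as non-responders for all subsequent days after rescue therapy start date". Case 3 treats scheduled assessments that go unobserved after study discontinuation or loss to follow-up as missing, so they become nonresponse through case 1.

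**Rescue definition.** SAP 11.3.9 opens with general words: "Rescue therapy will be defined as the addition of any new ITP medication or medication to treat thrombocytopenia (examples below"). It then states that "TPO receptor agonists are not allowed as rescue therapy" and gives a list, most of it with dictionary terms. The coded drugs are corticosteroids, immunoglobulins, anti-D, mycophenolate, azathioprine, danazol and ciclosporin. The only coded procedure is transfusion.

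**Prohibited therapies.** Protocol 6.5.1 says: "Some ITP therapies/procedures, such as vinca alkaloids, cyclophosphamide, rituximab, splenectomy, and other TPO-RAs (eltrombopag, romiplostim) are prohibited during the Primary Investigation Phase", and gives the reason and consequence as "due to their potential to confound efficacy results. Subjects requiring these therapies will be discontinued from the study". Protocol 5.3.1 lists treatment with the same therapies among the reasons for which "study drug may be permanently discontinued at the discretion of the Investigator". The lead sentence of protocol 5.3 is also permissive about study participation, and its reasons include needing a prohibited medication.

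**Which counts are used.** SAP 8.6 uses all assessments for cumulative and maximum duration, and SAP 11.1.1 confirms that unscheduled visits count. Protocol 5.3 asks for the EOT procedures when a subject terminates early.

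**The concern.** A subject who needs another TPO-RA, rituximab or a splenectomy during the Core Phase is most likely one in whom avatrombopag has not worked well enough. The protocol itself says that these therapies could confound efficacy. Yet the rule that protects the primary endpoint from other active treatment is tied to the word rescue, and it does not clearly extend to them.

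The handling is therefore uneven. A subject given IVIg scores no response from that date on. A subject given a splenectomy has no corresponding rule for any count taken before leaving the study. For the prohibited drugs, the answer depends on whether the programmer follows the general definition or the coded list.

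The trial has one arm, and success is judged by a lower confidence limit in the FAS. Misattributed response weeks would have no counterpart in a control group.

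**Working it through.** **Step 1. Is each prohibited therapy caught by the rescue rule?**

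| Therapy | General words of SAP 11.3.9 | Term in the coded list |
|---|---|---|
| Splenectomy | No: a procedure, not a medication | None (transfusion only) |
| Other TPO-RA | Can be read as yes; barred as rescue by the next sentence | None |
| Rituximab, vinca alkaloid, cyclophosphamide | Can be read as yes | None |

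The broad reading is reasonable but not secure. SAP 11.3.10, the next section, defines ITP medications for its own purpose as systemic corticosteroids only.

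**Step 2. Does case 3 catch what the rescue rule misses?** Only in part. It covers unobserved scheduled visits. A count taken after the therapy starts and before the subject leaves is observed, as is the early-termination EOT count. SAP 8.6 keeps both.

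**Step 3. The plan's own figure.** SAP section 6 and protocol 10.2.5 assume a mean of 12.0 weeks and an SD of 8.75, with a hurdle of 8.02 for the lower 95% limit and n = 19.

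- n = (1.96 × 8.75 / (12.0 − 8.02))² = 18.57, rounded up to 19. The stated size is reproduced.
- Normal-quantile lower limit at n = 19: 12.0 − 1.96 × 8.75/√19 = 8.07, about 0.05 above the hurdle.
- t-based lower limit: 12.0 − 2.101 × 8.75/√19 = 7.78, which is 0.24 below it.

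**Step 4. Size of the leak.** One subject wrongly credited with k weeks raises the mean of 19 by k/19. The documents give no value for k, so a range is assumed.

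| Credited weeks k (assumed, one subject) | Shift in mean, k/19 |
|---|---|
| 1 | 0.05 |
| 2 | 0.11 |
| 4 | 0.21 |

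SAP 11.1.1 computes duration as (last response day − first response day + 1)/7. Read literally, a single isolated responding EOT count adds 1/7 week, or (1/7)/19 = 0.008 week on the mean. Two responding counts seven days apart add 8/7 = 1.14 weeks, or 0.06 week on the mean. The upper end of the range needs several responding counts before withdrawal.

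**The case against.** The strongest reply is that the plan already deals with these subjects. Protocol 6.5.1 takes them out of the study in mandatory terms, and their later unobserved visits then become nonresponse. The list in SAP 11.3.9 is only a set of examples, so the absence of a code does not take a newly started drug out of the definition. The TPO-RA sentence restricts conduct; it does not tell the analyst to keep responses after a TPO-RA has been taken. Protocol 5.3.1 concerns study drug in both phases, whereas 6.5.1 concerns study participation in the Core Phase, so the two do not conflict head-on.

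Most of this stands, and it keeps the point small. It does not remove the point. Splenectomy remains outside the definition on any reading. Discontinuation does not reach counts already observed. Protocol 5.3 is permissive about participation itself, so the tension with 6.5.1 is not limited to study drug.

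Two stronger readings are tempting, and the documents support neither:

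- **Eight weeks from taper and follow-up visits (8/19 = 0.42 week).** A reader might infer that an early leaver attends these visits within the 26 weeks. Protocol 4.1 places them at the end of the Core Phase, and protocol 7.2.6 and 7.2.7 schedule them at Weeks 27 to 34. For early termination, protocol 5.3 asks only for the EOT procedures.
- **Sixteen weeks after a splenectomy at Week 10 (16/19 = 0.84 week).** This requires the subject to stay in the study contrary to protocol 6.5.1.

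**Conclusion.** The gap is real and narrow. Counts observed between the start of a prohibited ITP therapy or procedure and withdrawal, including the early-termination EOT count, can be credited to avatrombopag in the FAS primary endpoint. For splenectomy this follows from the text. For the drugs it depends on which reading of the rescue definition is programmed. The PPS may exclude such subjects (SAP 7.3 gives prohibited medication as an example), but that analysis is only supportive.

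With one affected subject and an assumed 1 to 4 credited weeks, the mean rises by 0.05 to 0.21 week; a lone EOT count adds less. The error runs in one direction.

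A reader might infer that responses to these treatments are systematically credited to the drug, or that one such subject would decide the trial. The documents do not show either. They give no frequency. The comparison with the hurdle uses planning inputs with the SD held fixed, and the thin margin at n = 19 is a sample-size matter that any small shift would expose. An effect on the Day 8 endpoint is unlikely, since the therapy and a response to it would both have to fall within about a week of the first dose.

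**What to change.** Add a fourth case to SAP 11.1.1, for example: *From the start date of any ITP therapy or procedure prohibited in protocol 6.5.1, all subsequent days are nonresponse, whether or not the subject remains under observation.*

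- Apply it also in SAP 11.3.1, 11.3.2 and the by-visit analyses in 11.3.6 to 11.3.8. The by-visit tables drop missing visits, so there it should be stated to act on observed counts.
- Add matching codes to the derivation for other TPO-RAs, rituximab, vinca alkaloids, cyclophosphamide and the splenectomy procedure. Protocol 6.5.1 introduces its list only by example, so the SAP should fix a closed list before Core Phase database lock.
- The sponsor should reconcile the permissive wording in protocol 5.3 and 5.3.1 with the mandatory wording in 6.5.1. Which of them applies is for the sponsor to decide.

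The cost is one sentence and one derivation from medication and procedure records that protocol 6.5 and 6.5.6 already require. The primary mean may become slightly less favourable.
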